8.1.2 Serious Adverse Event (SAE)

Any untoward medical occurrence that at any dose:

- Results in death
- Is immediately life-threatening
- Requires in-patient hospitalization
- Results in persistent or significant disability or incapacity
- Is a congenital abnormality or birth defect
- Is an important medical event that may jeopardize the subject or may require medical intervention to prevent one of the outcomes listed above.

Examples of possible SAE in our study:

- Respiratory depression which may be life-threatening and/or require prolonged hospitalization and/or result in persistent disability.
- Cardiovascular collapse secondary to respiratory depression or due to anaphylactic reactions or vasodilatation by other mechanisms.
- Anaphylactoid or anaphylactic reactions.

Medical and scientific judgment is to be exercised in deciding on the seriousness of a case. Important medical events may not be immediately life threatening or result in death or hospitalization, but may jeopardize the subject or may require intervention to prevent one of the listed outcomes in the definitions above. In such situations, or in doubtful cases, the case should be considered as serious. Hospitalization for administrative reason (for observation or social reasons) is allowed at the investigator's discretion and will not qualify as serious unless there is an associated adverse event warranting hospitalization.

8.1.3 Suspected Unexpected Serious Adverse Reaction (SUSAR)

Suspected Unexpected Serious Adverse Reaction: SAE (see section 8.1.2) that is unexpected as defined in section 8.2 and possibly related to the investigational medicinal product(s)..

This protocol has included a range of symptoms and vital signs, which are well-known side-effects/adverse events to all opioids, including the study medicines. Any such event mentioned in the protocol will be considered as SAE. Any event other than those mentioned in the SmPCs of the study medicines may be classified as SUSAR.

8.2 Expected Adverse Events

The following side-effects/adverse events: respiratory depression, sedation, nausea, vomiting, pruritus, dizziness and headache will be registered in the CRF.

Such AEs will be registered in the AE/SAE section of the CRF. Further adverse events listed in the SmPCs for the study drugs will also be registered as AE/SAE if they occur

- 1) Pentrox® 3 ml / ATC-nr. N02B G09/ Inhalation vapour, Mundipharma, Norwegian version section 4 "Bivirkninger".
- 2) Fentanyl® 2 ml, 0.05 mg/ml /ATC-nr. N01A H01/ intravenous use, Hameln, Norwegian version section 4 "Bivirkninger".

8.3 Time Period for Reporting AE and SAE

For each subject the standard time period for collecting and recording AE and SAEs will begin at start of study medicine and will continue until end of treatment as defined in paragraph 5.3.

For each patient the standard time period for collecting and recording AE and SAEs will begin at first session of four sessions and will continue for at least 1 h following the last dose of study treatment for each subject.

During the course of the study all AEs and SAEs will be proactively followed up for each subject; events should be followed up to resolution. Every effort should be made to obtain a resolution for all events, even if the events continue after discontinuation/study completion.

8.4 Recording of Adverse Events

If the patient has experienced adverse event(s), the investigator will record the following information in the CRF:

- The nature of the event(s) will be described by the investigator in precise standard medical terminology (i.e. not necessarily the exact words used by the patient).
- The duration of the event will be described in terms of event onset date and event ended data.
- The intensity of the adverse event: define as applicable the criteria used.
- The Causal relationship of the event to the study medication will be assessed as one of the following (the definitions below are according to WHO but can be deviated from if other/fewer categories are more suitable for the study):

Unrelated:

There is not a temporal relationship to investigational product administration (too early, or late, or investigational product not taken), or there is a reasonable causal relationship between non-investigational product, concurrent disease, or circumstance and the AE.

Unlikely:

There is a temporal relationship to investigational product administration, but there is not a reasonable causal relationship between the investigational product and the AE.

Possible:

There is reasonable causal relationship between the investigational product and the AE. Dechallenge information is lacking or unclear.

Probable:

There is a reasonable causal relationship between the investigational product and the AE. The event responds to dechallenge. Rechallenge is not required.

Definite:

There is a reasonable causal relationship between the investigational product and the AE.

- Action taken
- The outcome of the adverse event – whether the event is resolved or still ongoing.

It is important to distinguish between serious and severe AEs. Severity is a measure of intensity whereas seriousness is defined by the criteria in Section 8.1. An AE of severe intensity need not necessarily be considered serious. For example, nausea that persists for several hours may be considered severe nausea, but is not an SAE. On the other hand, a stroke that results in only a limited degree of disability may be considered a mild stroke, but would be an SAE.

8.5 Reporting Procedure

8.5.1 AEs and SAEs

All adverse events and serious adverse events that should be reported as defined in section 8.1.1 will be recorded in the patient's CRF.

SAEs must be reported within 24 hours after the site has gained knowledge of the SAE. Every SAE must be documented by the investigator on the SAE pages (to be found in the investigator site file). The investigator site file is as part of the CRF. The Serious Adverse Event Report Form must be completed, signed and sent to sponsor. The initial report shall promptly be followed by detailed, written reports if necessary. The initial and follow-up reports shall identify the trial subjects by unique code numbers assigned to the latter.

The sponsor keeps detailed records of all SAEs reported by the investigators and performs an evaluation with respect to causality and expectedness. Based on, among other, SAE reports the sponsor will evaluate whether the risk/benefit ratio associated with study is changed.

8.5.2 SUSARs

SUSARs will be reported to the Competent Authority (The Norwegian Medicines Agency and REK sør-øst C) according to national regulation. The following timelines should be followed:

The sponsor will ensure that all relevant information about suspected serious unexpected adverse reactions that are fatal or life-threatening is recorded and reported as soon as possible to the Competent Authority in any case no later than seven (7) days after knowledge by the sponsor of such a case, and that relevant follow-up information is subsequently communicated within an additional eight (8) days.

All other suspected serious unexpected adverse reactions will be reported to the Competent Authority concerned as soon as possible but within a maximum of fifteen (15) days of first knowledge by the sponsor.

SUSARs will be reported to The Norwegian Medicines Agency ([contact]) using the CIOMS form no later than 7 days after the incident.

Sponsor will also report SUSAR to the EMEAs EudraVigilance database. This may be done with assistance from Hameln or Mundipharma.

8.5.3 Annual Safety Report

Once a year throughout the clinical trial, the sponsor will provide the Competent Authority with an annual safety report. The format will comply with national requirements.

8.5.4 Clinical Study Report

The adverse events and serious adverse events occurring during the study will be discussed in the safety evaluation part of the Clinical Study Report.

8.6 Procedures in Case of Emergency

The investigator is responsible for assuring that there are procedures and expertise available to cope with emergencies during the study.

- The randomization code will be stored in [name]'s private office, Department of Anesthesiology, Oslo University Hospital, building 7, Ullevål. For safety reasons a sealed copy of the randomization code will also be available at the place where the study will be performed. This will be accessible 24/7. In case of an unexpected medical incident the code will be broken to ensure proper treatment. Each envelope with drugs will have a corresponding sealed envelope with the randomization code for the drug-envelope. This will enable us to identify the study medication given to one single subject without breaking the full randomization code.
- [name] (consultant anesthesiology, PhD) and [name] (anesthetist nurse) will be responsible for the implementation of the data. They are well trained in handling of patients with respiratory depression or other type of emergencies as part of professional training and practice.

Interventions if SpO₂ < 90% for more than 3 minutes or immediately if SpO₂ < 85% or respiratory rate < 8:

- 1) Stimulate patient to achieve respiratory rate > 8 and/or deeper respiratory action.
- 2) Supplemental oxygen to 2 l/min.
- 3) Reversal agent: Naloxone® (naloxone) 0.1 mg IV. Repeated every 2-5 minutes until response.
- 4) Bag-mask ventilation and consider other reasons for hypoxemia than opioid effect.

8.7 Data Monitoring Committee (DMC)

The investigator will be visited on a regular basis by the Clinical Study Monitor (Department of Clinical Research Support at Oslo University Hospital)

9 DATA MANAGEMENT AND MONITORING

9.1 Case Report Forms

For Electronic Case Report Forms (eCRFs) and paper Case Report Forms (pCRF)

The CRF for this study will be designed and produced by research nurse [name] and principal investigator [name], Oslo University Hospital.

The designated investigator staff will enter the data required by the protocol into the paper Case Report Forms (pCRF/CRF). The Investigator is responsible for assuring that data entered into the CRF is complete, accurate, and that entry is performed in a timely manner. The signature of the investigator will attest the accuracy of the data on each CRF. If any assessments are omitted, the reason for such omissions will be noted on the pCRFs. Corrections, with the reason for the corrections will also be recorded.

The data will be entered into a database and double-checked for erroneous entries. The setup of the database system will be performed by research nurse [name], Oslo University Hospital, Ullevål. Oslo University Hospital has a safe database (K. sensitive) where the data will be saved.

After database lock, the investigator will receive a digital copy of the subject data for archiving at the investigational site.

9.2 Source Data

Source data are all information in original records and certified copies of original records of clinical findings, observations, or other activities in a clinical trial necessary for the reconstruction and evaluation of the trial. Source data are contained in source documents (original records or certified copies).

The records for each subject should contain information, which is important for the subject's safety and to fulfill the requirement that critical study data should be verifiable

Specify and provide details if any source data will be recorded directly into the Case Report Form (meaning that for the defined parameters, CRF is source data and not the hospital records).

A source data list will be agreed upon for each site specifying the source at a module or a variable level.

9.3 Study Monitoring

The investigator will be visited on a regular basis by the Clinical Study Monitor (Department of Clinical Research Support at Oslo University Hospital), who will check the following:

- Informed consent process
- Reporting of adverse events and all other safety data
- Adherence to protocol
- Maintenance of required regulatory documents
- Study Supply accountability
- Facilities and equipments (example: laboratory, pharmacy, ECG machine, etc...) if applicable
- Data completion on the CRFs including source data verification (SDV).

The monitor will review the relevant CRFs for accuracy and completeness and will ask the site staff to adjust any discrepancies as required.

Sponsor's representatives (e.g. monitors, auditors) and/or competent authorities will be allowed access to source data for source data verification in which case a review of those parts of the hospital records relevant to the study will be required.

9.4 Confidentiality

The investigator shall arrange for the secure retention of the patient identification and the code list. Patient files shall be kept for the maximum period of time permitted by each hospital. The study documentation (CRFs, Site File etc) shall be retained and stored during the study and for 15 years after study closure. All information concerning the study will be stored in a safe place inaccessible to unauthorized personnel.

9.5 Database management

The data will be stored in a dedicated and secured area at:

- pCRF: in a locked filing cabinet in the office of research nurse [name] at the Department of Anesthesiology, Oslo University Hospital, building 7, Ullevål.

Data will be stored in a de-identified manner, where each study participant is recognizable by his/her unique trial subject number. The code list to link pCRF to patient in case of need for identifying data will be stored in a locked filing cabinet in the private office of research nurse [name] at the Department of Anesthesiology, Oslo University Hospital, building 7, Ullevål.

After transferal of data from pCRF to the database, the pCRF will be stored in the research archive at the Department of Anesthesiology, Oslo University Hospital, building 36, Ullevål.

- The database will be stored in the designated space in the secure research server for Oslo University Hospital (Domain "Felles"- "Sensitivt"; File "Forskning03").

The data will be stored until 31.12.2035.

Data management will be performed by research nurse [name] and principal investigator [name], Oslo University Hospital. The Data management procedures will be performed in accordance with the department's SOPs and ICH guidelines.

Data entered into the database will be validated by double-checking for erroneous entries against the CRF and hospital records.

10 STATISTICAL METHODS AND DATA ANALYSIS

10.1 Determination of Sample Size

The power analysis is based on data from one of our previous study using the same model, the cold pressor test.(13)

This is a crossover study. Data on standard deviation of differences between the conditions in a paired comparison is used in the calculation. nQuery Advisor software was used to calculate the sample size and to do the power analysis" A sample size of 10 will have 80% power to detect a difference in means of 0,500 (e.g. a First condition mean, of 6,000 and a Second condition mean of 5,500), assuming a standard deviation of differences of 0,500, using a paired t-test with a 0,050 two-sided significance level . We will include 12 subjects to achieve a more exact block-randomization.

10.2 Randomization

10.2.1 Allocation- sequence generation

Key elements to specify regarding allocation of treatment are:

- Method of generating the allocation sequence: computer-generated random sequential allocation. [name] [name] will generate the allocation sequence.
- Allocation ratio: 1:1.
- Type of randomization: blocked randomization. Details of blocked randomization are provided in a separate document that is unavailable to those who enroll subjects or assign treatment.

10.2.2 Allocation- procedure to randomize a subject

The study investigators will enroll the subjects. After the informed consent form is collected, the subjects will be allocated by choosing the next available treatment stored in sequentially numbered, opaque, sealed envelopes

10.2.3 Blinding and emergency unblinding

The investigators ([name] and [name]) and the subject will be blinded for the randomization and the study medication. The subject may theoretically identify the study medication from drug characteristics, but we consider this unlikely.

A doctor and a nurse will pack and label the study medicine. They will not be blinded, but will not participate in the handling of the subjects.

Emergency unblinding should generally only be done if the safety and well-being of the subject is being compromised. The decision to reveal the treatment allocation during the study should be done exclusively by the principal investigator.

Un-blinding of the treatment allocation is permissible only if the safety and well-being of the subject is being compromised. The decision to reveal the treatment allocation during the study may only be done by the principal investigator. The date and time of un-blinding must be documented in the CRF and in the patient's hospital records.

In the event of an SAE, the Investigator will break the treatment code.

10.3 Population for Analysis

The following populations will be considered for the analyses:

- The full analysis population: All randomized subjects having received at least one dose of study medication and where a minimum of data is collected.
- The per-protocol population: All randomized subjects completing the study without major protocol violations. Definition of major protocol violations will be specified in the statistical analysis plan, and the final criteria will be defined prior to database lock. Data concerning the primary endpoint should be collected.
- Safety population: Includes all randomized subjects who have received at least one dose of study medication. Subjects who withdraw from the study will be included in the safety analysis. A list of withdrawn subjects, preferably with the reasons for withdrawal, will be made.
- The primary statistical analysis will be based on the subjects meeting the definition of the protocol population according to inclusion and exclusion criteria and with no major protocol violations.
- The secondary analysis will include all patients receiving study treatment.

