6.2.4 Withdrawal Visit

If one participant experience very unpleasant or a severe adverse effect during a session, the session will be terminated. The participant will then be excluded from the rest of the study.

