6.4 Procedures for Discontinuation

6.4.1 Patient Discontinuation

Subject who gets any kind of severe adverse effects will be followed up.

All patients randomized will be included in the study population.

Patients who withdraw or are withdrawn from the study after randomisation cannot be replaced.

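### The completion condition in the per-protocol definition removes valid crossover sessions from the primary analysis, although the planned mixed model can use them

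*Combined protocol and SAP*

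**What the plan says.** Section 10.3 names the primary set: "The primary statistical analysis will be based on the subjects meeting the definition of the protocol population". The rest of that sentence mentions only eligibility and freedom from major violations. The definition of the per-protocol population in the same section adds completion: "All randomized subjects completing the study without major protocol violations". What counts as a major violation is left to a later SAP. Section 10.3 also plans a secondary analysis of everyone who received study treatment.

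Section 6.2.4 ends a session when an adverse effect is severe or highly unpleasant, and continues: "The participant will then be excluded from the rest of the study". Section 6.4.1 rules out replacement after randomization, yet also says: "All patients randomized will be included in the study population".

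Section 10.5.1 plans a linear mixed model for change from baseline in NRS, with the primary endpoint at the time-zero cold pressor test. Section 10.1 gives the power statement: "A sample size of 10 will have 80% power to detect a difference in means of 0,500", "assuming a standard deviation of differences of 0,500", "using a paired t-test with a 0,050 two-sided significance level". The reason given for enrolling more than 10 is not dropout: "We will include 12 subjects to achieve a more exact block-randomization".

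**The concern.** In a four-session crossover, completing the study is most naturally read as attending all four sessions. On that reading, a volunteer excluded during session 3 loses sessions 1 and 2 from the primary result as well, although nothing was wrong with them. The planned model does not need complete sequences, so the restriction gains nothing on the modelling side.

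Two things are at stake. First, removal happens after randomization and can depend on how the volunteer reacted to a drug. It therefore cannot be presumed random, and it can bias the methoxyflurane-fentanyl contrast. Second, with 12 volunteers and no replacement, each lost volunteer costs visible precision. The plan also does not say clearly which volunteers form the primary set: the primary-analysis sentence, the per-protocol definition and section 6.4.1 give three different impressions.

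**Working it through.** **1. The plan's own figure.** Inputs from section 10.1: difference 0.5, SD of differences 0.5, two-sided alpha 0.05, paired t-test. Power = P(|T| > t(0.975, n-1)), where T is noncentral t with n-1 degrees of freedom and noncentrality (0.5/0.5) x sqrt(n). At n = 10 the noncentrality is 3.162 and the critical value 2.262, giving 80.3%. The stated 80% is reproduced.

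**2. Power by number of completers** (same formula):

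| Completers | Lost of 12 | Power |
|---|---|---|
| 12 | 0 | 88.3% |
| 11 | 1 | 84.8% |
| 10 | 2 | 80.3% |
| 9 | 3 | 74.8% |
| 8 | 4 | 68.1% |

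The two volunteers above 10 absorb two losses. The third takes power below 80%.

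**3. Chance of three or more losses.** The documents give no stopping rate, so a range is assumed. With X ~ Binomial(12, p), P(X >= 3) = 1 - P(0) - P(1) - P(2):

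| Assumed p | P(X >= 3) |
|---|---|
| 5% | 2% |
| 10% | 11% |
| 15% | 26% |
| 20% | 44% |

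**4. Sessions discarded.** Suppose, as an illustration, a 20% chance of withdrawal after the fentanyl 0.05 mg session, with that session's endpoint recorded. This session is equally likely to fall in any of the four periods, and withdrawal after period 4 costs nothing. Expected losses are 12 x 0.20 x 3/4 = 1.8 volunteers, leaving 10.2 completers. Expected discarded sessions are 12 x 0.20 x (1 + 2 + 3)/4 = 3.6.

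**5. Completers only against all available sessions.** Simulation of a 12-subject, four-period Williams crossover, 2,500 runs per scenario. Assumptions not in the documents: between-subject SD 1.5, subject-by-drug SD 0.25, 20% withdrawal after each named session, no period effect, variances treated as known.

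Precision, with withdrawal unrelated to analgesic response. The half-width is that of the 95% interval for methoxyflurane minus fentanyl 0.05 mg; the miss rate is the chance of a non-significant result when the true difference is 0.5:

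| Withdrawal after | Half-width, completers | Half-width, all sessions | Miss rate, completers | Miss rate, all sessions |
|---|---|---|---|---|
| Fentanyl 0.05 mg | 0.323 | 0.310 | 13.1% | 10.3% |
| Fentanyl 0.05 mg or methoxyflurane | 0.358 | 0.328 | 20.6% | 14.7% |

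Bias, with side effects correlated 0.7 with analgesic response and a true difference of 0.5:

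| Withdrawal after | Stopped session's endpoint | Completers | All sessions |
|---|---|---|---|
| Fentanyl 0.05 mg | recorded | 0.456 | 0.481 |
| Methoxyflurane | recorded | 0.545 | 0.518 |
| Either | recorded | 0.495 | 0.493 |
| Fentanyl 0.05 mg | missing | 0.437 | 0.437 |
| Methoxyflurane | missing | 0.563 | 0.563 |

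Using all sessions roughly halves the bias when one drug drives withdrawal and the endpoint was captured. When withdrawals come from both drugs, the two estimates differ by no more than simulation noise. When the stopped session has no endpoint, all-session analysis leaves the bias unchanged.

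**The case against.** The strongest reply has four parts.

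- **The data are not lost to the trial.** Section 10.3 plans an all-treated secondary analysis, so the discarded sessions are reported there. This stands. But that analysis is not the primary one, and the plan has no rule for a disagreement between the two.
- **Per-protocol is a legitimate primary set for a margin hypothesis.** Section 10.5.1 states a 0.5-point margin. Adherence can vary, because volunteers inhale the dose themselves and must avoid analgesics and alcohol before each session. This also stands, and it is why moving the primary analysis to the full analysis population would be a trade-off rather than a plain gain. It justifies dropping a session with a violation. It does not justify dropping a sound session because a later one was stopped.
- **The completion condition is inferred.** The primary-analysis sentence does not contain it, and the only explicit four-treatment requirement is in section 10.5.2, for safety. This is correct. The condition enters through the per-protocol definition, and the ambiguity is itself a reason to edit.
- **With no withdrawals there is no effect.** True, and with one or two the loss is modest.

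A reader might also count volunteers stopped for unbearable cold-pressor pain under section 7.3. The documents do not clearly support that: section 7.3 stops the experiment but does not say that the volunteer leaves the study, and such stops could occur under any treatment, including control.

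**Conclusion.** The point holds as a defect in the definition of the primary set. On the natural reading of section 10.3, a volunteer excluded for an adverse effect takes valid sessions out of the primary result that the planned model could use. The power cost is small for one or two losses and falls below the planned 80% only from the third. How likely that is rests on a stopping rate that the plan does not give. The power-by-completers figures follow directly from section 10.1; the simulated figures are illustrative and rest on the assumptions listed.

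A reader might infer that the restriction tilts the result towards equipotence. The documents do not support a fixed direction. Withdrawals led by fentanyl move the estimate towards equality, withdrawals led by methoxyflurane move it away, and a mixture largely cancels. The precision loss also has no single direction, because section 10.5.1 leaves two tests unreconciled. If a non-significant difference were read as equipotence, falling from 12 to 10 completers would raise the chance of missing a true 0.5 difference from 11.7% to 19.7%. Under the 0.5-point margin hypothesis (one-sided 0.025, true difference zero), the same loss lowers the chance of success from 88.3% to 80.3%, which works against the claim. What remains is an avoidable bias of uncertain sign and an avoidable loss of precision.

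**What to change.** In section 10.3, strike the completion condition from the per-protocol definition and apply major violations by session. Every eligible randomized volunteer then contributes to the primary mixed model each session that has a valid time-zero cold pressor test and no major violation. List the session-level violations in the SAP before database lock. Keep the planned all-treated analysis alongside. Reconcile section 6.4.1, which places all randomized volunteers in the study population, with section 10.3.

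The cost is wording in the protocol and SAP. The model and data collection stay the same, and no stopping rule is touched. The limit is that a stopped session without an endpoint still leaves bias, so the report should give the number of such sessions and the treatment in each.
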